**Step 2: Sample parameters from the ML sampling distributions.**

Using the estimated ML multivariate sampling distribution from Step 1, we simulate (or sample) R sets of values and we denote one set for example as  $(\beta_0^*, \beta_1^*, k^*)$ . For subject  $i$ , the Weibull scale parameter will be computed on this set as

$$\gamma_i^* = \exp(\beta_0^* + \beta_1^* X_{li}).$$

This is done similarly for all R sets of sampled parameters.

**Step 3: Define and apply sensitivity parameter for each of two treatment groups.**

For subject  $i$  with censored time-to-event (ie,  $\delta_i = 1$ ), we define a sensitivity parameter  $c$  which is multiplied to the subject's hazard function estimated under CAR assumption, the new hazard function  $h_i^c(t)$  for time beyond the observed censored time-to-event ( $t > T_i$ ) represents the hazard under an alternative CNAR assumption:

$$h_i^c(t) = ch_i(t) = c \frac{kt^{k-1}}{\gamma_i^k} = \frac{kt^{k-1}}{(\gamma_i/(c^{1/k}))^k}$$

with the sensitivity parameter in the range of  $c > 0$ . If  $0 < c < 1$ , the CNAR hazard is lower than the CAR hazard and if  $c > 1$ , the CNAR hazard is higher than the CAR hazard. If  $c = 1$ , it is the same as the CAR hazard. Therefore, specifying a range of values in  $0 < c < 1$  and  $c > 1$  for this sensitivity parameter will represent a series of deviations from the CAR assumption in favorable and unfavorable directions respectively for time-to-event. Different sensitivity parameter  $c$  can be specified for different treatment groups.

**Step 4: Impute the time-to-event under a CNAR assumption ( $c$ ) using the sampled Weibull parameters.**

For subject  $i$  with censored time-to-event (ie,  $\delta_i = 1$ ) and with a specified CNAR sensitivity parameter  $c$ , using a single set of sampled Weibull parameters  $(\gamma_i^*, k^*)$  in Step 2, we can reconstruct the conditional predictive distribution as follows:

$$\gamma_i^{c*} = \gamma_i^* / (c^{1/k^*})$$

$$F_i^{c*}(t_i | t_i > T_i; c, \gamma_i^*, k^*) = 1 - \exp \left[ \left( \frac{T_i}{\gamma_i^{c*}} \right)^{k^*} - \left( \frac{t_i}{\gamma_i^{c*}} \right)^{k^*} \right].$$

In order to impute  $t_i$  (imputed value as  $t_i^*$ ), we generate one  $u_i^* \sim \text{Uniform}(0,1)$  for subject  $i$ , then we can solve for  $t_i^*$ ,

$$t_i^* | t_i > T_i = \gamma_i^{c*} \left[ \left( \frac{T_i}{\gamma_i^{c*}} \right)^{k^*} - \log(1 - u_i^*) \right]^{1/k^*}.$$

Different CNAR sensitivity parameter ( $c$ ) values will give different imputed  $t_i^*$  using the same  $u_i^*$  for this subject  $i$ .

The risk period and censoring time for imputation are defined for Sensitivity Analysis 1 and Sensitivity Analysis 2 separately:

Sensitivity Analysis 1:

The risk period for imputation is defined from the date of the randomization to the LSLV of Study A3921165, for subjects who are censored under the composite estimand.

Sensitivity Analysis 2:

- 1) the risk period for imputation is defined from the date of the randomization to the LSLV of Study A3921165, for subjects who are censored under the treatment policy estimand and not enrolled in the LTE study (Study A3921145);
- 2) the risk period for imputation is defined from the date of the randomization to the LSLV of Study A3921165 or to Randomization Day + 378 (the upper limit of the DB Week 52 visit window), whichever comes later, for subjects who are censored under the treatment policy estimand and enrolled in the LTE study (Study A3921145). “Randomization Day + 378” will include time spent post randomization in both Study A3921165 and Study A3921145. For example, if a subject is randomized on Study Day 80, then “Randomization Day + 378” is Study Day 458 and DB Phase Day 379; so imputation will be done up to max (LSLV of A3921165 – date of randomization + 1, DB Phase Day 379) for this subject enrolled in Study A3921145.

To implement the imputation constraint, if the imputed  $t_i^*$  is  $\leq$  the day of the end of risk period for imputation, the imputed time is used as is; if the imputed  $t_i^*$  is  $>$  the day of the end of risk period for imputation, the subject will be censored at the end of risk period for imputation. This can be performed for all subjects with  $\delta = 1$  and across all R sets of sampled Weibull parameters.

Step 5: Perform Rubin's rule for R complete imputed datasets.

For a given combination of sensitivity parameters specified for the treatment groups, Step 4 above will produce R sets of complete imputed datasets. Each of the complete imputed dataset will be analyzed using the unstratified log-rank test providing comparison of tofacitinib 5 mg BID versus placebo.

Each analysis above will give the Chi-squared test statistic (X) and degree of freedom (d) of a treatment comparison based on unstratified log-rank test. d is 1 if there are only two treatments in comparison across strata. The Wilson-Hilferty-transformed Chi-squared test statistic will be combined using Rubin's rules (Wilson and Hilferty, 1931; Moscovici and Ratitch, 2017; Ratitch, Lipkovich, and O'Kelly, 2013; Rubin, 1987). The Wilson-Hilferty transformation of the log-rank Chi-squared test statistic below, under null hypothesis of no treatment difference, will yield an asymptotic standard normal statistic (Z):

$$Z = \frac{\sqrt[3]{X/d} - (1 - 2/(9d))}{\sqrt{2/(9d)}}$$

with standard error of 1. These R sets of results will be combined via the Rubin's rules to obtain a combined Z that follows Student's t distribution according to the Rubin's rules and the upper-tailed 1-sided p-value corresponding to combined Z can be generated. The upper-tailed 1-sided p-value from the Student's t test of the Rubin's rules ([Ratitch, Lipkovich, and O'Kelly, 2013](#)) will then be compared to pre-specified 2-sided efficacy boundary ([Section 5.1](#)).

Step 6: Assessment of tipping points.

Step 5 above can be repeated for a range of sensitivity parameter ( $c$ ) values specified for each treatment group. The goal is to evaluate the impact of different CNAR assumptions for subjects with censored time-to-event on the conclusion. The specific implementation (ie, seeds for random number generation, number of multiple imputations (R), and values of the sensitivity parameter by treatment group) of this tipping point analysis will be specified in the statistical programming plan.

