## 5. GENERAL METHODOLOGY AND CONVENTIONS

### 5.1. Hypotheses and Decision Rules

The primary null hypothesis in this study is that there is no difference between the distributions of time to disease flare in the double-blind randomized withdrawal phase between tofacitinib and placebo. The alternative hypothesis is that, among the subjects that meet the randomization criteria, time to disease flare is increased in the subjects remaining on tofacitinib in the double-blind withdrawal phase versus placebo subjects.

The difference between the distributions of time to disease flare will be tested using an unstratified log-rank test ([Schoenfeld, 1987](#); [Shih, 1999](#); [Yang, 2012](#)).

There will be potentially 2 planned analyses. The First Analysis will be performed after 28 subjects have reported flare in the double-blind phase. Number of flares required for the 2 planned analyses will be counted according to the definition of having a flare in the primary estimand ([Section 2.3.1](#)). The purpose of the First Analysis is to allow early stopping of the study for efficacy or futility, and to assess safety of tofacitinib. The investigators, subjects, and sponsor study team will remain blinded to treatment assignment in the double-blind phase through the entire duration of the trial until final database release.

If the study does not end for efficacy or futility at the First Analysis, a total of 37 subjects with flares will be required for the Final Analysis to yield an overall power of 80% using a log-rank test to detect the treatment difference, assuming a 1-sided type-I error rate of 2.5% and a 64% improvement in median time to flare (i.e., a hazard ratio of 0.36 and a median time to flare of 236 days for placebo; assumptions based on a similar sJIA randomized withdrawal trial). The number of flares needed at the Final Analysis will be based upon the actual number of flares at the First Analysis (additional details are provided below and in [Appendix 2](#)).

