To protect the integrity of the study and to preserve the type I error rate at 0.025 (1-sided test) and overall study power at 80% (type II error rate  $\beta=0.2$ ), a fraction of  $\alpha$  for efficacy and a fraction of  $\beta$  for futility will be spent at the First Analysis and accounted for in the overall type I error rate and type II error rate, respectively. A formal efficacy boundary for rejecting the null hypothesis is constructed by using the spending function methodology of the gamma family design with  $\gamma= 4$ . Similarly, a formal futility boundary for not rejecting the null hypothesis is constructed by using the spending function methodology of the gamma family design with  $\gamma= -4$ .

- If the value of the test-statistic at the First Analysis crosses the efficacy boundary ( $z \leq -1.973$ , 1-sided  $p \leq 0.0242$ ), the trial may be stopped for efficacy.
- If the value of the test-statistic at the First Analysis crosses the futility boundary ( $z \geq -1.240$ , 1-sided  $p \geq 0.1074$ ), the trial may be stopped for futility.
- Otherwise, the trial will continue as planned. The Final Analysis will be performed after flares have been reported in 37 subjects.

**Table 2. Efficacy and Futility Stopping Boundaries with 28 Flares at First Analysis Expressed as Hazard Ratio, Z Scores and P-values**

Efficacy Stopping Boundary				
	Number of Flares	Hazard Ratio	Z-score	P-value (1-sided)
First Analysis	28	0.474	-1.973	0.0242
Final Analysis	37	0.427	-2.586	0.0049
Futility Stopping Boundary				
	Number of Flares	Hazard Ratio	Z-score	P-value (1-sided)
First Analysis	28	0.626	-1.240	0.1074

**Table 2. Efficacy and Futility Stopping Boundaries with 28 Flares at First Analysis Expressed as Hazard Ratio, Z Scales and P-values**

Final Analysis	37	0.427	-2.586	0.0049
----------------	----	-------	--------	--------

Assuming a hazard ratio of 0.36 (tofacitinib vs placebo) and a median time to flare of 236 days for placebo Randomization ratio = 1:1, type I error rate (1-sided) = 2.5%, power = 80.4%

Efficacy boundary: gamma family spending function with  $\gamma = 4$

Futility boundary (non-binding): gamma family spending function with  $\gamma = -4$

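### The tipping-point rule refers to a two-sided efficacy boundary that the SAP never states, and its pooled chi-square carries no direction of effect

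*SAP*

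**What the plan says.** SAP Section 5.1 sets a directional alternative: "time to disease flare is increased in the subjects remaining on tofacitinib in the double-blind withdrawal phase versus placebo subjects". The design is sized "assuming a 1-sided type-I error rate of 2.5" per cent. Table 2 gives the efficacy boundaries as hazard ratio, z-score and a p-value whose column heading begins "P-value (1-sided":

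- First Analysis, 28 flares: HR 0.474, z = -1.973, p = 0.0242.
- Final Analysis, 37 flares: HR 0.427, z = -2.586, p = 0.0049.

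Appendix 2 does the same for 29 to 31 flares at the first look, again one-sided. Protocol Section 10.1.1 treats one-sided 2.5% as equivalent to two-sided 5% overall, but it too states its First Analysis boundary one-sided.

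SAP Section 6.1.2.2 plans two tipping-point analyses, one for the composite estimand and one for the treatment policy estimand. Both are conditional on primary superiority; the second also requires Supplementary Analysis 2 to agree with the primary result. The hazard multipliers of the two arms vary independently over a two-dimensional grid. Both analyses pass through Appendix 5, Step 5, where "Each analysis above will give the Chi-squared test statistic (X) and degree of freedom (d) of a treatment comparison based on unstratified log-rank test". Next, "The Wilson-Hilferty-transformed Chi-squared test statistic will be combined using Rubin's rules", and "the upper-tailed 1-sided p-value corresponding to combined Z can be generated". That p-value "will then be compared to pre-specified 2-sided efficacy boundary", citing Section 5.1.

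Steps 5 and 6 give no value for that boundary, do not say which look it belongs to, and contain no rule on the sign of the effect. The number of imputations and the grid values are left to the programming plan.

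**The concern.** The rule that decides whether a grid cell still supports the primary conclusion has two gaps.

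**Threshold.** The cross-reference leads to a section with no two-sided boundary. A programmer who follows it finds 0.0242 and 0.0049. Set against a p-value that behaves as two-sided, these are too strict, and the primary result would look more fragile than it is.

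**Direction.** A chi-square is the same for benefit and harm. A cell in which the imputed data significantly favour placebo would be scored as showing a treatment effect, although the hypothesis under test is superiority of tofacitinib.

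The analysis runs only after a claimed success, and its purpose is to show how far that success depends on the censoring assumption. Its decision rule should be fixed before unblinding, not interpreted afterwards.

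**Working it through.** **1. Reproduce the plan's boundaries.** Inputs from SAP Section 5.1: one-sided alpha 0.025, gamma-family spending with gamma = 4, looks at 28 and 37 flares. With t = 28/37 = 0.7568, alpha spent = 0.025 × (1 - exp(-4t)) / (1 - exp(-4)) = 0.02423, so z = -1.973. Solving the final bound from the bivariate normal with correlation sqrt(t) and non-binding futility gives z = -2.586, p = 0.00485. The hazard ratio at a boundary is exp(-2|z|/sqrt(events)): 0.474 at 28 flares and 0.427 at 37. All match Table 2. The printed p-values are therefore one-sided, as labelled.

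**2. Scale of the Step 5 p-value.** For d = 1 the SAP's transform is Z = (X^(1/3) - 7/9) / sqrt(2/9), with X = z². The upper tail of Z, before pooling, compares as follows:

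| log-rank z | one-sided p | two-sided p | Wilson-Hilferty upper p |
|---|---|---|---|
| -1.973 | 0.0242 | 0.0485 | 0.0458 |
| -2.586 | 0.0049 | 0.0097 | 0.0095 |
| +1.973 | 0.9758 | 0.0485 | 0.0458 |

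The Step 5 p follows the two-sided log-rank p closely and is blind to sign.

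**3. What each choice of threshold demands.** Inverting the transform, |z| = (7/9 + Z_b × sqrt(2/9))^(3/2), where Z_b is the upper normal quantile of the threshold:

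| threshold used | required \|z\| | primary boundary \|z\| |
|---|---|---|
| 0.0242 (printed, 28 flares) | 2.233 | 1.973 |
| 2 × 0.0242 = 0.0484 | 1.950 | 1.973 |
| 0.0049 (printed, 37 flares) | 2.819 | 2.586 |
| 2 × 0.0049 = 0.0098 | 2.574 | 2.586 |

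As hazard ratios, the printed values would require exp(-2 × 2.233/sqrt(28)) = 0.43 instead of 0.474, and exp(-2 × 2.819/sqrt(37)) = 0.40 instead of 0.427. Doubled values return almost to the primary boundary.

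**4. Direction.** At z = +2.3, X = 5.29, X^(1/3) = 1.742, Z = (1.742 - 0.778)/0.471 = 2.05 and p is about 0.02, the same as for z = -2.3. Pooling does not restore the sign. With assumed per-imputation z of mean -2.5 or +2.5, SD 0.3 and 1,000 imputations, total variance is 1 + (1 + 1/R)B, where R is the number of imputations and B the between-imputation variance. The pooled Wilson-Hilferty p is then 0.0159 or 0.0164. Pooling the signed z gives one-sided p of 0.0083 or 0.9914.

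**5. Illustration on one simulated trial.** Assumptions, not from the documents: 27 per arm, uniform entry over 900 days, a quarter of subjects given a remission time between days 168 and 400, imputation to the date of the 28th flare, 500 imputations. Exponential times use the plan's placebo median of 236 days and HR 0.36. The chosen dataset had 28 flares and z = -2.38. Multipliers are given as tofacitinib, placebo:

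| multipliers | Wilson-Hilferty p | signed one-sided p |
|---|---|---|
| 1, 1 | 0.0172 | 0.0090 |
| 2, 1 | 0.0220 | 0.0116 |
| 5, 1 | 0.0356 | 0.0188 |
| 10, 1 | 0.0423 | 0.0223 |
| 20, 0.1 | 0.0659 | 0.0347 |

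Against 0.0242, the Wilson-Hilferty p tips between multipliers 2 and 5. Against 0.0484 it survives 10, and so does the signed p against 0.0242; both fail at (20, 0.1). No imputed dataset changed sign, even at multipliers 500 and 0.001.

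**The case against.** The strongest defence is that Step 5 is right as worded. The upper tail of a one-degree-of-freedom chi-square is a two-sided test, and the SAP asks for a two-sided boundary. Table 2 labels its p-values one-sided and also prints z-scores, so doubling is an obvious step, and the protocol itself equates one-sided 2.5% with two-sided 5%. This stands as far as it goes. A reader might infer that the SAP sets a two-sided p against a one-sided limit; the text does not say that. The mismatch appears only if the printed column is used. Still, the rule cites a pre-specified number that is specified nowhere, and does not say which look it comes from.

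On direction, moving from significant benefit to significant harm means crossing a non-significant band, so along any path outward from the censoring-at-random point the tipping point is met first. In Sensitivity Analysis 1, imputation stops at last subject last visit, so subjects censored at study end have little time to impute. This stands too. It limits the problem to extreme cells, but such cells would still be labelled wrongly if run.

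Two further readings go too far:

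- Under HR 0.36 at 28 flares, P(z ≤ -1.973) = 0.767 and P(z ≤ -2.233) = 0.681. A reader might infer that (0.767 - 0.681)/0.767, about 11%, of First Analysis successes would fail with no departure from random censoring. That figure requires the one-sided column to be used, and it ignores imputed flares and between-imputation variance, so it is not a result at c = 1.
- A reader might call this the only planned check on informative censoring. Supplementary Analysis 2 uses observed off-treatment and extension-study flares to Week 52, and has its own tipping-point analysis, although that shares Step 5.

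**Conclusion.** The point holds as a defect in the decision rule of a sensitivity analysis. Two-sided is the correct scale; the threshold is missing and the cross-reference leads only to one-sided values. If those values were used, the required |z| would be about 2.23 instead of 1.973 at 28 flares, or 2.82 instead of 2.586 at 37, and the tipping point would be declared too early. These figures treat a single log-rank z; Rubin's rules add between-imputation variance to either choice.

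The loss of direction is real but narrow: it matters only in cells where the imputed effect is near zero or reversed. Whether such cells will be run, and so whether any cell would be mislabelled, cannot be determined from the documents, because the grid and the number of imputations are not given. The documents do not support the inference that a reversed effect would pass as robust.

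The primary log-rank test, its boundaries and its type I error are not affected. The correction is worth making before unblinding because it is almost free and removes a choice that would otherwise be made after a positive result.

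**What to change.** In SAP Appendix 5, Step 5, pool the signed log-rank Z (standard error 1) across imputations with Rubin's rules. Compare its one-sided p, in the direction of tofacitinib benefit, with the one-sided boundary of the look at which superiority was declared, as recalculated under Section 5.1.

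If the Wilson-Hilferty form is kept, state the threshold as twice that one-sided boundary: 0.0484 at 28 flares, 0.0098 at 37, or twice the recalculated value. Count a cell as supportive only if the pooled effect also favours tofacitinib.

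Either version serves both tipping-point analyses. The cost is a few words in Appendix 5 and a minor programming change; no other analysis is touched.

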## Appendix 6. List of Abbreviations

Abbreviation	Term
ACR	American College of Rheumatology
AE	adverse event
aJIA	adapted juvenile idiopathic arthritis
AST	aspartate aminotransferase
bDMARD	biologic disease modifying antirheumatic drug
BID	twice daily
CAR	censoring at random
CCC	Centralized Coordinating Center
CHAQ	Childhood Health Assessment Questionnaire
CHAQ-DI	Childhood Health Assessment Questionnaire-Disability Index
CHQ	Childhood Health Questionnaire
CI	confidence interval
CL/F	oral clearance
CNAR	censoring not at random
COVID-19	corona virus disease 2019
CRF	case report form
CRP	C-reactive protein
CS	corticosteroids
CSH	heterogeneous compound symmetry
CV	cardiovascular
DB	double-blind
DBFAS	double-blind full analysis set
DBSAS	double-blind safety analysis set
DSMB	Data Safety Monitoring Board
EAC	Endpoint Adjudication Committee
EOT	end of treatment
ESR	erythrocyte sedimentation rate
FDA	Food and Drug Administration (United States)
GI	gastrointestinal
GIPRC	Gastrointestinal Perforation Review Committee
HERC	Hepatic Event Review Committee
HR	hazard ratio
HZ	herpes zoster
ICH	International Council for Harmonisation
ILDRC	Interstitial Lung Disease Committee
IR	incidence rate
JADAS	juvenile arthritis disease activity score
JIA	juvenile idiopathic arthritis
K-M	Kaplan-Meier
LOCF	last observation carried forward
LOE	lack of efficacy
LS	least squares

Abbreviation	Term
LSLV	last subject last visit
LTE	Long term extension
MAC	Malignancy Adjudication Committee
MAS	macrophage activation syndrome
MCP	metacarpophalangeal
MedDRA	Medical Dictionary for Regulatory Activities
ML	maximum likelihood
MMRM	mixed model for repeated measures
MR	missing response
MTX	methotrexate
NR	non response
OI	opportunistic infection
OIRC	Opportunistic Infection Review Committee
OL	open-label
OLPT	open-label part
PIP	proximal interphalangeal
pcJIA	polyarticular course juvenile idiopathic arthritis
PK	pharmacokinetic(s)
RA	rheumatoid arthritis
RP	risk period
SAE	serious adverse event
SAP	statistical analysis plan
SDAC	Statistical Data Analysis Center
SE	standard error
SI	serious infection
sJIA	systemic juvenile idiopathic arthritis
SOC	system organ class
SOP	standard operating procedure
SUN	Standard Uveitis Nomenclature
TEAE	treatment-emergent adverse event
TFL	table figure listing
US	United States
VAS	visual analog scale
WHO	World Health Organization
